5.1 Administration Schedule

NOTE: All patients should be on at least 81 mg acetylsalicylic acid (ASA) daily while receiving lenalidomide. Please see Section [5.6.16](#) for additional information regarding thromboprophylaxis.

5.1.1 **Arm X (Arms A and B)**

NOTE: Patients are randomized to Arm A (lenalidomide and ixazomib) or Arm B (lenalidomide and placebo) but will be identified as on Arm X as this is a blinded trial.

Lenalidomide: 10 mg PO daily days 1-28

NOTES: For patients with creatinine clearance 30-60 mL/min lenalidomide dose will be reduced to 5 mg PO daily.

Lenalidomide may be taken with or without food. Capsules must not be crushed, chewed, or opened.

Please refer to Section [8.2](#) for additional Lenalidomide administration details.

Ixazomib/Placebo: 4 mg PO days 1, 8, and 15

Repeat cycle every 28 days until disease progression or unacceptable toxicity.

NOTES: Ixazomib/Placebo capsule(s) must be taken on an empty stomach, 1 hour before or 2 hours after food. Capsule(s) must be swallowed whole with water. Do not open or break capsules.

Missed or delayed doses can be taken only if the next scheduled dose is \geq 72 hours away. A missed dose should not be taken within 72 hours of the next scheduled dose. If vomiting occurs after taking a dose, the patient should not repeat the dose. Resume dosing at the time of the next scheduled dose.

Please refer to Section [8.1](#) for additional Ixazomib/Placebo administration details.

Rev. Add3

Rev. Add3

Rev. Add3

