9.2.2 Patient-Reported Outcomes

9.2.2.1 Primary Endpoint

- Change in FACT/GOG-Ntx TOI score calculated as the difference after completion of 12 cycles of study therapy from baseline
- Change in FACT-MM TOI score calculated as the difference after completion of 24 cycles of study therapy from baseline

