9.2.2.3 Exploratory Endpoints

- Presence, frequency, interference, amount and/or severity of select PRO-CTCAEs tabulated at each cycle
- ASK-12 scores at each assessment time point
- PRO compliance rate defined as the proportion of patients who submit the given PRO instrument among those eligible at each time point which excludes those missing by design (due to death or disease progression, early treatment discontinuation)
- PRO completion rate defined as the proportion of patients who complete given PRO instrument based on the instrument's scoring system among those eligible at each time point

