9.3.2 Secondary Clinical Analyses

Progression-Free Survival (PFS)

An important secondary aim is to evaluate whether a response-adapted strategy translates into superior progression-free survival for patients switching to more-intensive treatment. PFS will be estimated using the KM method and compared using the stratified log-rank test. Median PFS on the control arm is assumed to be 18 months based on results from recent clinical trials. Assuming exponential distribution of failures, this study is design to detect a 44% increase in median PFS to 26 months on the experimental arm. This corresponds to a treatment HR approximating 0.70 [monthly hazard rate 0.0385 versus 0.0267]. At 1-sided 2.5% type I error, there is approximately 90% power using a log-rank test to detect this HR given 510 patients uniformly accrued over 3.5y with full information of 319 PFS events at 4.5y (accrual end plus one year). The actual timing of this PFS analysis will depend on accrual. The analysis will not be done before one year after the last patient is randomized. No interim analyses for the PFS comparison will be conducted. The study team will also not consider or declare the experimental arm to be a success based on the PFS endpoint alone.

Response

Response will be tabulated by category. Response rates (sCR, CR, VGPR) will be compared using the chi-squared test for proportions. It is hypothesized that the ixazomib-lenalidomide arm will have higher response rates. Ineligible patients are excluded from the analysis and unevaluable patients are counted in the denominator. Sensitivity analyses will exclude unevaluable patients from the rate calculations. Given 255 patients per arm, there is over 90% to detect a difference of 15% in VGPR rates at 1-sided 2.5% significance assuming a 52.5% overall VGPR rate.

Toxicity

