9.3.4 Patient-Reported Outcomes (PRO) Endpoints

PRO compliance and completion rates will be tabulated at each collection time point and overall separately for the FACT-G (FWB and PWB subscales), FACT-Ntx, FACT-MM, ASK-12 and PRO-CTCAE instruments.

Health-Related Quality of Life (QOL)

To assess the impact of treatment and disease on health-related QOL, there are two co-primary endpoints: change in FACT/GOG-Ntx TOI from baseline to end of cycle 12 post-randomization (beginning of cycle 13 assessment) and change in FACT-MM TOI from baseline to end of cycle 24 (beginning of cycle 25 assessment) post randomization. The FACT-G (FWB and PWB subscales), Ntx and MM will be administered at the beginning (day 1) of every 3 cycles for the first 24 cycles (beginning of cycles 4, 7, 10, 13, 16, 19, 22 and 25) and every 6 cycles thereafter (up to completion of 48 cycles of therapy (beginning of cycles 31, 37, 43, and 49), or at treatment discontinuation prior to completion of 48 cycles of therapy. During long-term follow-up/post-treatment end, there will be four quarterly assessments for 1 year. We hypothesize that treatment with ixazomib will not result in a significant difference in the FACT/GOG-Ntx TOI over the first 12 cycles and that improved PFS will result in higher FACT-MM TOI scores by end of 24 cycles. All patients who receive at least one dose of study drug and complete the QOL assessment at both time points are eligible. Power calculations are based on t-tests comparing the two treatment arms for the change in score with a 2-sided 0.05 alpha split between these comparisons. In an unselected group of MM patients being treated with oral therapy (n=118), the FACT-MM TOI had a standard deviation (SD) of approximately 21 points. The FACT-Ntx TOI has a reported SD of 14-16.⁷⁰ We propose using a general effect size measure of half standard deviation to establish the minimally important difference (MID).^{47,69} We therefore will establish a MID of 10 for the FACT-MM TOI and 8 for the FACT-Ntx TOI. We assume 90% and 81% of patients are alive by year 1 and 2, respectively, as well as a 10% drop-out rate resulting in potential patients of n=414 and n=373 for each analysis. Sensitivity for the proportion assumed to submit the questionnaire at both time points (compliance rates of 60% and 80%), allowing for a range of instrument variability and assuming different correlation (0.6, 0.4) between repeated measures was performed (Table 3). The difference in the FACT-Ntx TOI mean change score over 12 cycles of treatment between the ixazomib-lenalidomide arm and the placebo-lenalidomide arm that can be detected with 80% power at 2-sided 0.025 significance level ranges from 3.7-6.9 points as shown below. The difference in the FACT-MM TOI mean change score over 24 cycles of

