
treatment between the ix-a lenalidomide arm and the placebo-lenalidomide arm that can be detected with 80% power at 2-sided 0.025 significance level ranges from 5.8-10.0 points. All of the scenarios show the target MID for each comparison or smaller can be detected with satisfactory power and thus we will be able to show a significant difference in QOL if it occurs.

Table 3

			Differences in FACT-Ntx TOI Subscale Mean Change Score (power=80%, 2-sided alpha=0.025)	
Standard Deviation (SD)	Correlation	SD of change	60% compliance (n=124/arm)	80% compliance (n=164/arm)
From Baseline to 12 Cycles Post Randomization				
12.0	0.6	10.7	4.2	3.7
	0.4	13.1	5.2	4.5
14.0	0.6	12.5	4.9	4.3
	0.4	15.3	6.0	5.3
16.0	0.6	14.3	5.6	4.9
	0.4	17.5	6.9	6.0
Differences in FACT-MM TOI Mean Change Score (power=80%, 2-sided alpha=0.025)				
Standard Deviation (SD)	Correlation	SD of change	60% compliance (n=112/arm)	80% compliance (n=148/arm)
From Baseline to 24 Cycles Post Randomization				
18.0	0.6	16.1	6.7	5.8
	0.4	19.7	8.2	7.1
20.0	0.6	17.9	7.4	6.4
	0.4	21.9	9.1	7.9
22.0	0.6	19.7	8.2	7.1
	0.4	24.1	10.0	8.7

Sensitivity analysis will be conducted to retain patients who discontinued treatment early and missing their FACT-Ntx TOI score after 12 cycles of treatment (beginning of cycle 13 assessment) using their QOL score at early treatment discontinuation for the analysis. For the FACT-MM TOI analysis after 24 cycles of treatment (beginning of cycle 25 assessment) the long-term follow-up assessment closest to 2 years from randomization will be used if patients are not on treatment. Descriptive statistics (mean, SD, median, range) will be used to evaluate the distribution of levels and

changes for the set of health-related QOL evaluations including the FACT/GOG-Ntx TOI, FACT-MM TOI and FACT-G (FWB and PWB subscales). Levels and changes will also be assessed graphically. Linear mixed effects models will be used to perform repeated measured regression analysis with the assumed covariance matrix maximizing Akaike information criteria. Models with treatment, assessment time, and treatment by assessment time interaction with and without other predictors will be fit. If there is substantial missingness, we will analyze the data according to the methods described in Schluchter and Schluchter, Greene and Beck. These methods consider missingness informative by jointly modeling longitudinal QOL score and survival time to dropout.

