9.4 Sample Size Considerations

Rev. Add1

OS will be estimated based on the KM method and compared between arms using the stratified log-rank test. All survival estimates are from randomization, which would be ~18 months from start of initial therapy. Median OS for the control arm was estimated to be 5.5 years (y) considering expectations in this setting for an unselected cohort as well as results from the previously mentioned meta-analysis according to post-treatment MRD status.³ Based on the log-rank test, there is approximately 80% power at 1-sided 2.5% significance to detect a difference in 4y OS from 60.4% to 72.2% reflecting an approximate 35% reduction in hazard [treatment HR=0.65] assuming 510 patients uniformly accrued over 3.5y and 179 deaths at full information (6y).

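### Table 3 makes no allowance for progression: the potential FACT-Ntx N is about 321 to 357, not 414 (the MID is still met), and the FACT-MM and year-1 SUVmax figures depend on off-treatment rules that the plan leaves unsettled

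*Combined protocol and SAP*

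**What the plan says.** Section 9.3.4 sets the sample for the patient-reported endpoints with "We assume 90% and 81% of patients are alive by year 1 and 2, respectively, as well as a 10% drop-out rate", giving 414 patients for FACT-Ntx TOI (12 cycles) and 373 for FACT-MM TOI (24 cycles). It then applies 60% or 80% compliance, described there as the share submitting the form at both time points. Table 3 gives detectable differences of 3.7-6.9 and 5.8-10.0 points, and the text concludes that the MIDs of 8 and 10 can be detected in every scenario.

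On treatment length, Section 5.1 says "Repeat cycle every 28 days until disease progression or unacceptable toxicity". Section 9.3.2 says "Median PFS on the control arm is assumed to be 18 months based on results from recent clinical trials", with 26 months on the experimental arm. Section 9.2.2.3 defines the compliance rate "among those eligible at each time point which excludes those missing by design (due to death or disease progression, early treatment discontinuation").

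For FACT-Ntx, early stoppers return only in a secondary step: "Sensitivity analysis will be conducted to retain patients who discontinued treatment early and missing their FACT-Ntx TOI score".

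For FACT-MM, Section 9.2.2.1 has "Change in FACT-MM TOI score calculated as the difference after completion of 24 cycles of study therapy from baseline", while Section 9.3.4 has "change in FACT-MM TOI from baseline to end of cycle 24 (beginning of cycle 25 assessment) post randomization". Section 9.3.4 adds that patients off treatment contribute the follow-up score nearest to 2 years, without saying whether this governs the main test. Section 6.3.2 ends follow-up questionnaires one year after treatment stops.

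For year-1 SUVmax, Section 12.1.3.2 allows 15% for missing or unreadable scans.

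**The concern.** Patients who progress come off treatment and have no cycle-13 on-treatment score. The plan's own PFS assumption makes this a much larger loss than the deaths it counts, yet no factor in the sample-size chain is stated to cover it. Compliance as Section 9.2.2.3 defines it has already excluded these patients. The detectable differences would then be too favourable. For FACT-MM, the set of scores in a co-primary test would also be open to choice after the data are seen. If on-treatment scores alone counted, more control than experimental patients would be lost, although the plan's hypothesis is that better PFS raises scores. The same question affects the year-1 scan comparison, a secondary imaging aim.

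**Working it through.** **1. Reproduce the plan's N.** Inputs from Section 9.4: control median OS 5.5 years, HR 0.65, exponential. Alive at 1 year: 88.2% and 92.1%, mean 90.15%. Alive at 2 years: 77.7% and 84.9%, mean 81.30%.
- 510 × 0.9015 × 0.90 = 413.8 (stated 414)
- 510 × 0.8130 × 0.90 = 373.2 (stated 373)

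So 90% and 81% are deaths only. With the stated n per arm (124, 164, 112, 148), a two-sample t-test at two-sided 0.025 and 80% power returns Table 3 to within about 0.1 point.

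**2. Progression-free fraction.** S(t) = exp(−ln 2 × t / median). Twelve 28-day cycles are 11.04 months; 24 are 22.08 months.
- 12 cycles: 65.4% control, 74.5% experimental, mean 69.9%
- 24 cycles: 42.7% and 55.5%, mean 49.1%

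PFS already counts deaths, so OS is not applied again.

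**3. FACT-Ntx.**
- Drop-out separate from progression: 510 × 0.699 × 0.90 = 321 (150 control, 171 experimental)
- Drop-out overlapping progression: 510 × 0.699 = 357

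Detectable difference ≈ SD × √(2(1−ρ)) × (2.241 + 0.842) × √(1/n₁ + 1/n₂). Worst cell (SD 16, ρ 0.4, 60% compliance, n 90.0 and 102.6): 17.53 × 3.083 × 0.1444 = 7.80, or 7.9 with the noncentral t. All cells, in Table 3 order:
- 60%: 4.8, 5.9, 5.6, 6.9, 6.4, 7.9
- 80%: 4.2, 5.1, 4.9, 5.9, 5.6, 6.8

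At 357 the range is 3.9-7.5. No cell exceeds 8. The lowest power at 8 points, with 321, is 82%.

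**4. FACT-MM.**
- *Follow-up scores count:* 373 is about right. By month 9, however, 29.3% and 21.3% have had a PFS event and 9.0% and 6.0% have died, so about 20% of control and 15% of experimental patients are alive with progression. If they stop treatment by then, their last scheduled questionnaire falls at or before month 9 + 12 = 21, at least 3 months short of 2 years.
- *On-treatment scores only:* N = 510 × 0.491 × 0.90 = 225, or 251 without the 10%. At 225 the detectable differences are 8.7, 10.6, 9.7, 11.8, 10.6, 13.0 (60%) and 7.5, 9.2, 8.3, 10.2, 9.2, 11.2 (80%). Six of 12 exceed 10; at 251, five do. Three of the six are near misses (10.2, 10.6, 10.6; power at 10 points 74-78%). With 90-100% compliance in the pool of 225, one of six SD/correlation cells exceeds 10.

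**5. SUVmax.** Residual SD 10 × √(1−0.45) = 7.42, difference 2.0, two-sided 0.05 (sidedness assumed). At 217 per arm power is 80.0%, as stated. If scans stop with treatment:
- 167 and 190 patients (no other loss): 72%
- 142 and 161 patients (a further 15% lost): 65%

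Power of 80% holds up to SD 9.0 and 8.3 respectively. At SD 8 it is 89% and 83%.

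**The case against.** The best reply is that Section 9.2.2.3 defines a reporting rate, whereas Section 9.3.4 describes its own factor as submission at both time points. A patient with no cycle-13 form because of progression is a non-submitter, so 60%/80% could already absorb progression. This stands in part. The 60% FACT-Ntx column needs 248 patients, which is 77% of 321 or 69% of 357, and is attainable. The 80% column needs 328, which is more than 321 and about 92% of 357. So the reply rescues one column but leaves the other doubtful.

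Drop-out is also undefined, so 321 is not a firm figure. Nor is it a floor, because it deducts nothing separately for toxicity stops.

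A reader might infer that FACT-MM is underpowered. The documents do not establish that. The follow-up-score sentence in Section 9.3.4 is the most specific text. Eligibility there requires one dose and both questionnaires, not continued treatment, and Section 1.4.2 expects year-2 scores to reflect recurrence. What remains is that the sentence directly follows one on sensitivity analysis, that Section 9.2.2.1 points the other way, and that no time window is given.

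A reader might likewise take 65-72% as the SUVmax power. No section says that scans stop with treatment. Section 12.1.1 and footnote 12 of Section 7.1 tie them to completed cycles. Section 1.5.3 counts cycles from study entry, Section 12.1.1 opens by expecting scans of all registered patients, and Section 4.5 withholds later imaging only from those never treated. SD 10 is also the plan's upper case.

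**Conclusion.** The FACT-Ntx sample size is too favourable: about 321 potential patients, or 357 if drop-out overlaps progression, against 414. With compliance as Section 9.2.2.3 defines it, detectable differences are about 4.2-7.9 (3.9-7.5) rather than 3.7-6.9. This rests on the plan's exponential PFS medians, 28-day cycles and treatment ending at progression. It does not overturn the FACT-Ntx conclusion, since the MID of 8 is met throughout. For FACT-MM and SUVmax the finding is an unresolved rule, and the less favourable figures apply only under one reading of each. The OS primary design is not touched. The point is worth correcting, but it does not threaten the trial's main result.

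**What to change.** 1. Restate the FACT-Ntx N and the Table 3 rows with attrition from the Section 9.3.2 PFS curve, and say what drop-out and compliance each include.
2. Reconcile Sections 9.2.2.1, 9.2.2.3 and 9.3.4 on whether off-treatment scores enter the main FACT-MM test. If they do, keep 373 and give a window around 2 years that takes account of the one-year limit in Section 6.3.2. If they do not, restate the FACT-MM rows and the claim that every scenario detects the MID.
3. Reconcile Sections 1.5.3, 4.5, 7.1 (footnote 12) and 12.1.1 on whether year-1 scans continue after treatment stops, and restate the SUVmax power only if they do not.

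The planned mixed and joint models can stay. The cost is SAP wording and recalculated figures, with no new data, no change of test and no change to the OS design. Some stated figures become less favourable. Settle the FACT-MM rule before unblinding, so that the analysis set is not chosen with the data in view.

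### Section 9.3.4 picks the covariance structure of the longitudinal QOL models by maximizing AIC; on the usual AIC scale that selects the worst-fitting candidate and can give wrong standard errors, and the plan defines no larger-is-better form

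*Combined protocol and SAP*

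**What the plan says.** On the longitudinal analysis of the FACT scores, section 9.3.4 states: "Linear mixed effects models will be used to perform repeated measured regression analysis with the assumed covariance matrix maximizing Akaike information criteria". The mean model is given in the next sentence: "Models with treatment, assessment time, and treatment by assessment time interaction with and without other predictors will be fit". The section states no AIC formula or scale, no software, no list of candidate structures and no method for the standard errors. If much data is missing, it turns to joint models of score and dropout time, for which it states no AIC rule.

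Section 9.2.2.2 lists score levels and changes since baseline, for all instruments, as a secondary PRO endpoint. Apart from those joint models, the mixed model is the only inferential longitudinal method named for it.

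The other QOL comparisons are described separately. On the main ones the section says "there are two co-primary endpoints: change in FACT/GOG-Ntx TOI from baseline to end of cycle 12 post-randomization"; the second is the FACT-MM TOI change to the end of cycle 24. It adds: "Power calculations are based on t-tests comparing the two treatment arms for the change in score with a 2-sided 0.05 alpha split". The two key secondary comparisons, time to worsening and time to improvement, use Kaplan-Meier and log-rank. The adherence regressions are fitted at 12 and at 24 cycles separately.

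**The concern.** AIC trades fit (logL) against the number of parameters (p). Written as −2logL + 2p, better models have smaller values, and the structure to choose is the one that minimizes it. A rule that maximizes this quantity chooses the candidate that AIC ranks last.

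The covariance structure drives the model-based standard errors of the arm and arm-by-time contrasts. If too little within-patient correlation is modelled, a difference averaged over visits looks more precise than it is, and a within-patient change looks less precise than it is. The first error makes false positives more likely. The second makes a real worsening harder to detect, which matters because the plan's own hypothesis is that ixazomib causes no significant difference in the FACT/GOG-Ntx TOI.

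**Working it through.** **1. The plan's own figures.** No stated figure depends on the AIC rule. The nearest is Table 3, which gives differences "that can be detected with 80% power at 2-sided 0.025 significance level ranges from 3.7-6.9 points" for the FACT-Ntx TOI and 5.8 to 10.0 points for the FACT-MM TOI. The formulas are SD of change = SD × √(2(1 − ρ)) and detectable difference = SD of change × √(2/n) × (2.241 + 0.842).

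- SD 12, ρ = 0.6, n = 124 per arm: SD of change = 12 × √0.8 = 10.73, and 10.73 × √(2/124) × 3.083 = 4.20 (stated 4.2).
- The exact t calculation over all cells gives 3.67 to 6.90 (Ntx) and 5.79 to 9.99 (MM). Every cell agrees within 0.06 points.

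Table 3 reproduces, and the covariance rule plays no part in it.

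**2. Closed-form illustration.** Inputs from section 9.3.4: "assuming different correlation (0.6, 0.4) between repeated measures was performed"; "The FACT-Ntx TOI has a reported SD of 14-16", of which 14 is used; 124 patients per arm. Assumed here: the truth is compound symmetry, and independence is among the candidates and is selected.

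- Change contrast, model SE / true SE = 1/√(1 − ρ): 1/√0.6 = 1.29 for ρ = 0.4, and 1/√0.4 = 1.58 for ρ = 0.6.
- Difference averaged over m visits, ratio = 1/√(1 + (m − 1)ρ). With m = 5 (baseline and cycles 4, 7, 10, 13): 1/√2.6 = 0.62 and 1/√3.4 = 0.54.

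**3. Simulation.** There were 1,000 trials per scenario, with 124 per arm, five visits, SD 14, no missing data and no arm effect. The truth was compound symmetry (CS) or AR(1) with ρ = 0.4 or 0.6. The candidates were independence, CS, AR(1) and unstructured, and then the same list without independence. Maximizing −2logL + 2p chose one wrong structure in 1000/1000 runs of every scenario:

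| Candidates | Truth | Chosen | SE ratio, change (ρ 0.4; 0.6) | Type I | SE ratio, average (ρ 0.4; 0.6) | Type I |
|---|---|---|---|---|---|---|
| With independence | CS | Independence | 1.28; 1.57 | 0.016; 0.003 | 0.62; 0.54 | 0.227; 0.266 |
| With independence | AR(1) | Independence | 1.01; 1.07 | 0.046; 0.030 | 0.72; 0.62 | 0.162; 0.212 |
| Without | CS | AR(1) | 1.27; 1.47 | 0.015; 0.003 | 0.85; 0.87 | 0.094; 0.094 |
| Without | AR(1) | CS | 0.89; 0.82 | 0.093; 0.091 | 0.99; 0.99 (rounded down from 0.995) | 0.039; 0.046 |

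Type I error is at nominal 5%; its Monte Carlo standard error is √(0.05 × 0.95/1000) = 0.007.

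**4. The two corrected readings.** Minimizing −2logL + 2p chose the true structure in 97.7% to 98.7% of runs, with SE ratios of 0.99 to 1.00 and type I error of 0.040 to 0.062. Maximizing logL − p made the same selections, as it must: −2 × (logL − p) = −2logL + 2p.

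**The case against.** The strongest reply is that the sentence may not be wrong at all. On the logL − p form, maximizing is correct, and the plan names neither formula nor software. A competent analyst would probably pick the best-fitting structure whatever the wording. Both points are fair. They make the fault conditional, but they do not remove it: a prespecified rule should have one reading, and this one has two opposite ones.

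Three stronger inferences are tempting, and the documents do not support them.

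- *That every longitudinal QOL result would have a wrong standard error.* Even on the reversed reading, some contrasts are nearly right: 1.01 for change under AR(1) with ρ = 0.4, and 0.99 for the average when CS is chosen under AR(1). Robust standard errors would also protect; the plan does not say whether they will be used.
- *That a nominal 5% test would reject 34% to 42% of the time.* With m = 9 (baseline plus eight visits to cycle 25), √(1 + 8ρ) is 2.05 to 2.41, and 2Φ(−1.96/2.05) to 2Φ(−1.96/2.41) is 0.34 to 0.42. This needs independence as a candidate, one constant correlation over nine complete visits, and a visit-averaged contrast including baseline. The plan names no such contrast and lists no candidates. It uses 0.4 and 0.6 only for the paired change calculation, and it allows for 60% to 80% compliance. A mixed model with a random patient intercept would already carry within-patient correlation.
- *That the main QOL conclusions are at risk.* The co-primary endpoints are two-time-point changes. The plan says that their power rests on t-tests without expressly naming the t-test as the analysis, but that is the natural reading, and nothing ties them to the AIC rule.

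**Conclusion.** The point holds as a wording fault in a stated analysis rule, of modest importance. On the usual AIC scale, section 9.3.4 read literally reverses the choice of covariance structure, and nothing in the plan defines the form on which the wording would be right.

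The consequence can be wrong standard errors for longitudinal arm and arm-by-time contrasts, in either direction. Over the four simulated situations the ratio of model to true standard error ran from 0.82 to 1.57 for a change contrast and from 0.54 to about 1 for a visit-averaged difference. These ranges rest on assumed true structures, assumed candidate lists, five complete visits and model-based standard errors, because the plan supplies none of these. They illustrate the fault and do not forecast the trial's error rates.

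The reach is limited to the mixed models. The co-primary change-score comparisons, the Kaplan-Meier and log-rank QOL analyses, the single-time-point regressions, Table 3, OS and PFS do not use the rule.

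**What to change.** In section 9.3.4, replace *maximizing* with *minimizing* and state the form: the structure with the smallest AIC, where AIC = −2logL + 2p. If the larger-is-better form is intended, define it as logL − p and keep the present verb. It would also help to list the candidate structures and the standard-error method, but this is optional.

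Prespecifying an unstructured matrix with a fixed fallback order would avoid selection altogether. That is a preference, not a correction: it needs 9 × 10/2 = 45 covariance parameters for baseline plus eight visits, or 13 × 14/2 = 91 for all 13 scheduled assessments to cycle 49, and choosing by AIC is a legitimate approach once the direction is right.

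The cost is one sentence, with no effect on data collection, sample size or power.
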